2.2 Overview of COPTIC study design

COPTIC is a prospective observational study of patients undergoing cardiac surgery at the Bristol Heart Institute.

- i. All participants undergo standard pre-operative, anaesthetic, surgical and post-operative care according to existing protocols.
- ii. Blood samples are obtained in the operating theatre at the following time-points:

STATISTICAL ANALYSIS PLAN

[figure not shown]
COPTIC: Coagulation and platelet laboratory testing in cardiac surgery
A prognostic study of associations between post-operative test results and subsequent bleeding

- a. Immediately before induction of anaesthesia (*pre-operative sample; 9.5mls*)
- b. Immediately after reversal of heparin anticoagulation (*post-operative sample; 18.5mls*)

Data are collected until 12 hours after admission to Cardiac intensive care unit (CICU). The study timings are shown in Figure 1.

Figure 1: Timeline for COPTIC study

T0: time of pre-op sample

T1: cessation of CPB

T2: administration of final routine dose of protamine

T3: time of post-op sample

T4: time of arrival in CICU

T5: 6 hours after arrival in CICU

T6: 12 hours after arrival in CICU

T7: CICU discharge

Interval 1 time interval between pre-op and post-op samples [T3-T0]

Interval 2a post-op sample to 6 hours after admission to CICU [T5-T3]

Interval 2b post-op sample to 12 hours after admission to CICU [T6-T3]

Interval 2 time interval between post-op sample and CICU discharge [T7-T3]

This SAP refers to the analysis of post-operative Multiplate test results, ROTEM test results and TEG test results (part of Study B). A separate analysis plan will be written for the analyses of the other laboratory results from post-operative samples (also Study B).

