3.6 Analysis populations

The analysis population will be defined as all eligible, consenting patients who provided a post-operative blood sample. The final datasets will be restricted to those with laboratory assay results from the post-operative sample, and CRF data and clinical data extracted from PATS and INNOVIAN in order to define the primary outcome. Any consenting patients who had a post-operative sample collected but did not undergo surgery for medical or other reasons will be excluded from the analysis population. Comparisons between those in the final analysis population and those with CRF data and clinical data extracted from PATS and INNOVIAN in order to define the primary outcome, a pre-operative sample taken but incomplete laboratory assay results will be compared using standardised mean differences.

Involvement in any other UHBristol Clinical Trials and Evaluation Unit (CTEU) studies will be reviewed and any interventions deemed to have an impact will be reported. Details on how this information will be recorded are given in [section 6.4](#).

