4. COPTIC DATA COLLECTION

4.1 Data sources

Information will be collected from the following sources:

Data sources and identification details for linkage

Data type	Brief description	Identification for linkage
CRF Data	Information on time samples were taken, time of CICU admission, blood loss 6 and 12 hours post CICU admission, red blood cells (RBC) and non-RBC transfusions during operation and post-	STUDYID (identifies patient), COPTIC SAMPLEID (identifies sample), operation date, Hospital number/BRI Trust number

STATISTICAL ANALYSIS PLAN

COPTIC: Coagulation and platelet laboratory testing in cardiac surgery
A prognostic study of associations between post-operative test results
and subsequent bleeding

Data type	Brief description	Identification for linkage
	operatively up to CICU admission.	
Clinical data	Data extract from PATS Database including reoperation details (Section 5.1 (iii) and clinical outcomes as detailed in Section 2.5 (c).	Hospital number/BRI Trust number, name, sex, date of birth, operation date
Clinical data	Data extract from INNOVIAN, clinical information system of hourly data for time spent in CICU. These data include red blood cells (RBC) and non-RBC transfusions during CICU admission and clinical outcomes as detailed in Section 2.5 (c).	Hospital number/BRI Trust number, operation date
Clinical data	Creatinine test results for all consenting COPTIC patients, restricted to the closest test prior to the operation (pre-op) and any tests after the operation but within 7 days of the operation date (post-op)	BRI Trust number, date of birth
Laboratory test results	Results from all laboratory tests detailed in Section 2.5.1. These are transferred from the coagulation lab as a single file (FBC) or in the form of many separate files of weekly results (Multiplate, TEG and ROTEM).	All post-operative samples are identified by the COPTIC SAMPLEID (as in CRF data). The date of test will also be used to aid linkage.

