5. DEFINITIONS

5.1 Clinical concern about bleeding

The main objective of this prognostic study is to estimate how well test results from the post-operative blood samples predict CCB, i.e. bleeding that is likely to cause direct patient harm or indirect patient harm by precipitating a non-routine pro-haemostatic treatment or re-operation for bleeding for which no direct surgical cause is identified.

A participant will be classified as having experienced the primary outcome of CCB if any of the three circumstances below is documented within the designated time interval:

- i. Post-operative blood loss (volume collected through chest drain) greater than 600mL at T5¹ (interval 2a).
- ii. Intervention with a non-routine early pro-haemostatic treatment (EPT) defined as additional protamine after initial heparin reversal during interval 2b², fresh frozen plasma (FFP), cryoprecipitate, platelets, anti-fibrinolytic drug, recombinant human coagulation factors VII [rFVII] or fibrinogen concentrate during interval 2b (T3-T6 ; Figure 1).

¹ Chest drain volume after 6 hours from admission to CICU is likely to be an unreliable marker of actual bleeding because of contamination with tissue fluid. There is no universally effective threshold for clinical concern about post-operative bleeding even at T5, so 600 ml total during this interval is a pragmatic clinical suggestion. Chest drain volumes at T6 will continue to be collected but it is very difficult to suggest a plausible 'threshold' value at this time point that will reflect 'actual bleeding'.

² Medical notes and details for those patients who only received additional doses of protamine and no other non-RBC products will be reviewed. Those with only one dose of protamine, administered after the post-operative sample is collected but prior to admission to CICU will be considered "routine" administration of protamine. The medical notes for all other instances will be reviewed and the protamine will be classified as "routine" or "therapeutic" as appropriate. Those considered to have received "routine" dose(s) of protamine will not be included in the definition of EPT.

STATISTICAL ANALYSIS PLAN

COPTIC: Coagulation and platelet laboratory testing in cardiac surgery
A prognostic study of associations between post-operative test results and subsequent bleeding

- iii. Reoperation for bleeding recorded during hospital stay and failure to demonstrate a surgical cause for bleeding³.

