6. DERIVATIONS

6.1 Primary endpoint

The rules and data sources for the primary endpoint of CCB are as follows:

New variable	Rules	Data sources
CCB (binary)	If post-operative blood loss 6hrs post CICU admission > 600mL OR intervention with a pro-haemostatic treatment (see section 5.1 for the definition) during interval 2 [interval 1 or interval 2b for therapeutic protamine] OR reoperation for bleeding where no surgical cause for bleeding is identified.	CRFs (blood loss data) PATS (return to theatre due to suspected bleeding) INNOVIAN clinical information system and CRFs (transfusion data) PATS (rFVII) Haematology Department (rFVII and fibrinogen concentrate)

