6.2 Secondary endpoints

New variable	Rules	Data sources
RBC transfusion	Any RBC transfusion during interval 2	INNOVIAN clinical information

⁵ Diagnosis, evaluation, and management of acute kidney injury: a KDIGO summary (Part 1). Kellum *et al.* Critical Care 2013, 17:204

STATISTICAL ANALYSIS PLAN

COPTIC: Coagulation and platelet laboratory testing in cardiac surgery
A prognostic study of associations between post-operative test results and subsequent bleeding

New variable	Rules	Data sources
(binary)	(the time between post-operative samples are taken and discharge from CICU).	system
RBC >4 units (binary)	Any RBC transfusion >4 units during interval 2 (the time between post-operative samples are taken and discharge from CICU).	INNOVIAN clinical information system
Non-routine pro-haemostatic treatments (binary)	Any platelet, FFP, cryoprecipitate or rFVII transfusion during intervals 1 and 2 (the time between post-operative samples are taken and discharge from CICU), or therapeutic protamine during interval 2b (the time between post-operative samples are taken and 12 hours post CICU-admission).	INNOVIAN clinical information system and CRFs
Serious post-operative complications:		
Death (binary)	Vital status (alive vs. died in theatre OR died in hospital).	PATS Database (updated with NSTS data)
MI (binary)	Any MI occurring before discharge OR death from MI in hospital.	PATS Database, INNOVIAN clinical information system and death certificate data
Stroke (binary)	Any peri- OR post-operative neurological complication (stroke; transient ischaemic attack; hemiplegia; paralysis; paraplegia; dysphasia; cerebral/CNS infarct/embolus).	PATS Database, INNOVIAN clinical information system
AKI (binary)	Serum creatinine increased by ≥ 26.5 $\mu\text{mol/l}$ from the pre-operative value within 48 hours of surgery OR serum creatinine increased ≥ 1.5 times the pre-operative value within 7 days of surgery.	Creatinine data
Infection during hospital admission (binary)	Any infective complication (chest infection; wound infection; mediastinitis; graft site infection; sternal wound infection; urinary tract infection; septic; sepsis; blood borne infection).	PATS Database and INNOVIAN clinical information system

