7.2 Specific analysis procedure

The approach is to evaluate the separate platforms (Multiplate/preop; ROTEM; TEG; Multiplate/postop) individually in the first instance, and then evaluate whether the inclusion of additional platforms would improve this. The reason for considering groups of variables by platform (rather than simply choosing the 'best' subset of variables) is because there is no cost of using extra variables from one platform, but an extra cost of doing a second test. The specific steps are as follows:

- Step 1 Review the prediction achieved by patient characteristics. Define an optimal model based only on "baseline" covariates⁶. There will be a separate model for
- **any CCB** (intra-operative or post-operative) and
 - **post-op CCB** only
- Comment: We expect these models to be consistent with one another, not least because the majority of events (post-op CCPB events) will be common to both models.*
- Step 2 Review of each test platform to obtain the best model for each, including the baseline covariates:
- pre-operative Multiplate in relation to **any CCB** (this model is interesting in its own right, but from a slightly different perspective, i.e. it allows the care team to make a plan to mitigate the risk of CCB or to prepare to manage it)
 - pre-operative Multiplate in relation to **post-op CCB**
 - post-operative Multiplate in relation to **post-op CCB**
 - post-operative ROTEM in relation to **post-op CCB**
 - post-operative TEG in relation to **post-op CCB**
- Comment: Each of these models will consider all variables for the test/timepoint, i.e. consider the test/timepoint as a "package." The first model stands alone for **any CCB**. For **post-op CCB**, this step will identify which of the latter four models is the best platform for predicting CCB, i.e. provides the best prediction. We hypothesise that the best platform will be one of the post-op platforms because the information from these is more 'proximal' to the outcome for these models, i.e. **post-op CCB**.*
- For the best test/timepoint** (assuming there is one best test), we will also investigate whether a model using test variables that are available early (for the test identified as best) performs as well as a model using the standard test variables available at "test completion."

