⁶ These are: age, sex, diabetic status (n/y), cardiac procedure (CABG only, CABG + valve, valve alone, other), operative priority (elective, urgent), eGFR, preoperative HCT, treatment group, time since withdrawal (anti-platelet group), body mass index (BMI), preoperative platelet function and participation in another clinical study.

- Step 3 Test whether the addition of one of the other (post-operative) platforms improves this best model for **post-op CCB**. In practice, this is likely to be a test of whether Multiplate-post improves prediction compared to either ROTEM or TEG (or, adding ROTEM or TEG to Multiplate-post, since ROTEM and TEG are assessing similar mechanisms and Multiplate is assessing different ones). The combination of ROTEM and TEG together will not be considered.
- For the test/timepoint** added at Step 3 (assuming that there is one), we will also investigate whether a model using test variables that are available early (for the test/timepoint added at Step 3) performs as well as a model using the standard test variables available at “test completion.”
- Step 4 Test whether the addition of the pre-operative Multiplate platform improves the model identified in Stage 3.
- If Multiplate-pre** is added at Step 4, we will also investigate whether a model using test variables that are available early for Multiplate-pre performs as well as a model using the standard test variables available at “test completion.”

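### Models 2C to 2E make no provision for pro-haemostatic treatment given before the T3 sample, and post-op CCB, their outcome, is never derived

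*SAP*

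**What the plan says.** **Timing.** SAP 2.2 defines "Interval 1 time interval between pre-op and post-op samples [T3-T0"], so interval 1 covers everything before the post-operative sample.

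**Population.** Section 3.6: "The analysis population will be defined as all eligible, consenting patients who provided a post-operative blood sample". Section 3.5 reviews samples only for their timing against cell saver or pump blood and routine protamine.

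**Outcome.** Section 7.2, Step 1, separates any CCB ("intra-operative or post-operative") from post-op CCB and expects most, not all, events to be common to both. Models 2C to 2E use post-op CCB. The treatment windows differ between sections:
- 5.1 ends its list of products with "fibrinogen concentrate during interval 2b (T3-T6 ; Figure 1").
- 6.1 counts treatment "during interval 2 [interval 1 or interval 2b for therapeutic protamine"].
- 6.2, for the secondary endpoint, has "Any platelet, FFP, cryoprecipitate or rFVII transfusion during intervals 1 and 2", followed by an explanation in brackets that describes interval 2 only.

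**Covariates.** Footnote 6 of 7.2 lists the baseline set, ending with "eGFR, preoperative HCT, treatment group, time since withdrawal (anti-platelet group), body mass index (BMI), preoperative platelet function and participation in another clinical study". The list in 2.7 also has no treatment given before T3. Section 2.3 says that intra-operative factors will be considered as potential confounders. Section 7.3 puts the baseline characteristics into one score with its coefficient fixed at 1.00.

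**Data.** Section 4.1 says the CRF holds "red blood cells (RBC) and non-RBC transfusions during operation" and up to CICU admission.

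**The concern.** Platelets, plasma, cryoprecipitate or fibrinogen given before T3 can change the T3 results, and they are more likely to go to patients who are already bleeding. Such treatment comes before the test, so it is not on the path from test to outcome. It plausibly meets the SAP's own description of a confounder (footnote 7 to 7.4.2). Section 3.5 accepts that the circumstances of sampling can invalidate a result, but does not extend this to products already given.

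At stake is the reading of the odds ratios. Section 7 states the main objective as the strength of association between post-operative results and CCB. If treated and untreated patients are pooled without distinction, the estimate may mix the effect of coagulopathy with that of earlier treatment. If an event before T3 can make someone a case, part of the outcome comes before the test meant to predict it.

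**Working it through.** **1. Is treatment before T3 handled anywhere?** I traced it through the population (3.5, 3.6), the covariates (2.7, footnote 6, 7.4.2), model building (7.3) and the sensitivity analyses (7.4.6, 7.4.7). It is not. The sensitivity analyses change how treatment enters the outcome; none concerns treatment before the sample. The statement in 2.3 is not carried into either covariate list.

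**2. How would such a patient be classified?** Of the three CCB criteria, drain loss at T5 and re-operation fall after T3, so only the treatment criterion can precede the test.

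| Patient, with no later event | 5.1 | 6.1 |
|---|---|---|
| Platelets between T0 and T3 only | non-case | non-case |
| Therapeutic protamine in interval 1 only | non-case | case, event before test |

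Post-op CCB is a third quantity with no rule of its own. The T3 sample is taken in theatre (2.2), so it is also unclear whether the boundary between intra-operative and post-operative is T3 or the end of the operation.

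**3. How large could the effect be?** The SAP has no figure to reproduce: it gives neither the number treated before T3, nor the effect of treatment on results, nor the CCB rate. All inputs below are assumptions, with 400,000 patients per scenario and higher test values meaning worse coagulopathy.

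*Model A.* Latent coagulopathy C ~ N(0,1). Treatment T has logit a + C, with a set to give 5%, 10% or 20% treated. Test = C − d·T + noise (SD 0.5). Outcome logit = b + ln 2·(C − r·T), with b set for 25% CCB. Odds ratios are per unit of test.

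| Treated | d (test) | r (risk) | OR ignoring T | OR excluding treated | AUC ignoring / excluding |
|---|---|---|---|---|---|
| 20% | 1 | 1 | 1.71 | 1.71 | 0.652 / 0.652 |
| 20% | 0 | 0 | 1.74 | 1.71 | 0.664 / 0.653 |
| 20% | 1 | 0 | 1.66 | 1.70 | 0.645 / 0.651 |
| 10% | 1 | 0 | 1.69 | 1.71 | 0.652 / 0.656 |
| 5% | 1 | 0 | 1.71 | 1.71 | 0.656 / 0.658 |

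The change is at most about 0.03 to 0.04 in odds ratio and about 0.01 in AUC.

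*Model B* adds residual risk that the test does not show. Treatment has OR 2.5 per SD of z. Test = z − s·T + noise (SD 0.5). Outcome logit = −1.3 + 0.6·(z − s·T) + e·T. Odds ratios are per SD of test.

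| Treated | s | e | OR ignoring | adjusting | excluding |
|---|---|---|---|---|---|
| 20% | 1.5 | 0 | 1.67 | 1.66 | 1.66 |
| 20% | 1.5 | 1.2 | 1.46 | 1.66 | 1.66 |
| 20% | 0 | 1.2 | 1.92 | 1.66 | 1.66 |
| 10% | 1 | 1.2 | 1.61 | 1.67 | 1.67 |

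Repeat runs differ by about 0.02. The value e = 1.2 is an odds ratio of exp(1.2) = 3.3 for treated against untreated patients with the same coagulopathy after treatment. At 5% treated and e = 0.6 the range is 1.65 to 1.75 ignoring treatment, against 1.66 to 1.70 adjusting. The direction turns on s: the estimate is too low when treatment corrects the test strongly and too high when it does not move the test.

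**The case against.** The strongest reply is that the plan is largely predictive. For prediction, the T3 value is the patient's actual state when a decision would be made, whatever was given before; keeping everyone also preserves the representativeness that 7.4 stresses. This stands for the prediction reading and is a good reason to leave the main population alone. It does not answer the association reading, which section 7 calls the main objective.

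Four stronger readings are tempting, and the documents do not support them:
- *Treated patients are counted as CCB-free controls.* This follows from 5.1, but post-op CCB is not derived, and 6.1 would make some of these patients cases.
- *Section 6.2 shows that the SAP counts products given before T3.* Its bracketed explanation describes interval 2 only, so the mention of interval 1 may be a slip.
- *The odds ratios are materially biased.* A test altered by treatment is not enough: with e = 0 in Model B the difference is about 0.02 or less. Large shifts need a substantial assumed residual risk as well, and the extremes need 20% treated.
- *The choice of best platform is distorted.* The simulations hold one test and no platform-specific input, so they say nothing about ranking.

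**Conclusion.** The point holds as a gap in specification. Models 2C to 2E neither exclude, flag nor adjust for pro-haemostatic treatment between T0 and T3, contrary to the intent stated in 2.3, and their outcome has no derivation while the windows in 5.1, 6.1 and 6.2 conflict. These findings rest on the text alone.

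The size and direction of any bias cannot be obtained from the SAP. Under the assumed inputs it runs from nothing to about 0.2 to 0.26 in the odds ratio (1.66 − 1.46 = 0.20; 1.92 − 1.66 = 0.26). The upper end applies only if many patients were treated and they kept risk that the test does not show. That justifies a clear outcome definition and an inexpensive robustness check, not a change of the main population.

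**What to change.** 1. Derive post-op CCB explicitly so that it counts only events after T3, and reconcile the windows in 5.1, 6.1 and 6.2.
2. Report how many patients received non-routine pro-haemostatic treatment between T0 and T3, with their T3 results shown separately.
3. Keep all patients in the main analysis of Models 2C to 2E and add two sensitivity analyses: (a) a yes/no term for such treatment in both the baseline comparator and the platform models, so that its own predictive value is not credited to the test; (b) exclusion of these patients.

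Making the restricted set the main analysis is not needed: adjusting and excluding gave the same odds ratios to within 0.01 in the Model B scenarios shown. Sections 7.3 and 7.4.7 already describe some work in the past tense, so it could also be a post-hoc change of population.

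The cost is SAP wording, one derived variable and some extra analysis. The CRF records transfusions in theatre, and 6.4 already distinguishes doses by period. Two rules must be written: how to classify products not timed against T3, and what counts as non-routine in interval 1, since 5.1 defines this only for interval 2b.

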It is already known that anti-platelet drugs cause abnormal results in some laboratory tests of platelet function. Some other factors may also influence platelet function tests. It is unknown whether any laboratory test or combination of tests of platelet function can be used to predict CCB. The overall aim of the COPTIC Study B is to estimate the association between the results from a panel of laboratory tests of platelet function and count performed after cardiac surgery and CCB in all patients. Since anti-platelet drugs have marked effect of some platelet laboratory tests, we will also estimate the association between test results and CCB in patient subgroups (no anti-platelet drugs vs. aspirin alone vs. aspirin plus P2Y₁₂ blockers). We will also estimate the association between test results and duration of withdrawal of P2Y₁₂ blockers and the relationship between duration of withdrawal of P2Y₁₂ blockers and CCB. Other pre-operative, intra-operative and post-operative factors (up to T6) will be considered as potential confounders of the association between platelet test results and CCB. Estimates of association will be used to generate a parsimonious predictive model of the probability of CCB based on post-operative platelet test results and other factors.

The specific study objectives are as follows:

1. In all patients:
 - (a) to describe the distributions of post-operative test results ('primary predictors' and 'secondary predictors', see [section 2.6](#)).
 - (b) to examine the relationship between post-operative test results and the primary clinical outcome of CCB (see [section 5.1](#)).
2. In the patient sub-groups *no anti-platelet drugs, aspirin alone* and *aspirin+ P2Y₁₂ blockers*:
 - (a) to describe the distributions of post-operative test results ('primary predictors' and 'secondary predictors')
 - (b) to examine the relationship between i) post-operative test results and ii) the primary clinical outcome of CCB (see [section 5.1](#)).
3. In the patient sub-group *aspirin+ P2Y₁₂ blockers*:
 - (a) to describe the distributions of duration of withdrawal of P2Y₁₂ blocker

STATISTICAL ANALYSIS PLAN

COPTIC: Coagulation and platelet laboratory testing in cardiac surgery
A prognostic study of associations between post-operative test results and subsequent bleeding

(b) to examine the relationship between the duration of withdrawal of P2Y₁₂ blocker and post-operative test results.

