6.4 Other variables

More can be entered here

STATISTICAL ANALYSIS PLAN

COPTIC: Coagulation and platelet laboratory testing in cardiac surgery
A prognostic study of associations between post-operative test results and subsequent bleeding

New variable	Rules
Age	(Operation date – DOB)/365.25
BMI	Weight (kg) / Height (cm) ² * 10,000
Time in theatre	Cumulative bypass time; cumulative cross-clamp time
Cardiac procedure	CABG, Valve, other (or combination)
Pre-operative kidney function	Pre-operative serum creatinine and dialysis information will be used to calculate estimated glomerular filtration rate (eGFR): Cockcroft-Gault formula: $eC_{Cr} = \frac{(140 - \text{Age}) \times \text{Mass (in kilograms)} \times [0.85 \text{ if Female}]}{72 \times \text{Serum Creatinine (in mg/dL)}}$ Or, when serum creatinine is measured in $\mu\text{mol/L}$: $eC_{Cr} = \frac{(140 - \text{Age}) \times \text{Mass (in kilograms)} \times \text{Constant}}{\text{Serum Creatinine (in } \mu\text{mol/L)}}$ where Constant is 1.23 for men and 1.04 for women.
Blood products as units	Divide volume (ml) by 280 to obtain red cells units Divide volume (ml) by 225 to obtain platelet units Divide volume (ml) by 260 to obtain FFP units Divide volume (ml) by 175 to obtain cryoprecipitate units Selected as averages of given NHSBT product specifications NB: Calculation of total units will be defined as missing if the total doses=0 and any of intra-op, grey area, INNOVIAN data are missing. i.e. they will not be recorded as missing if any doses given at any of these times is recorded, even if data at least one other time are missing.
Operative priority	This will be defined as “elective” or “urgent”. Any few emergency or salvage procedures will be classified as urgent.
Cardiac procedure	This will be classified in four groups; CABG only; CABG+valve; Valve alone; other
Involvement in other studies	An indicator will be created for each trial as follows: 
 (Y/N) for participation in HARVeST, PROMPT, VERDICT, Protection1 (n/liberal group/restrictive group) for TITRe2 (n/intervention group/control group) for PASPORT There will be no indicator for concurrent involvement in smaller trials.

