7.3 Model fitting

Models will be fitted first for the standard time frame. Then, models will be fitted for the rapid time frame (see [Table 2.6.3](#)), testing whether this results in a “significant” deterioration in prediction. Comparing rapid and standard time frames is interesting because there may be a trade-off between potential benefits of earlier decision making (e.g. allows definitive treatment to be provided more quickly, thereby preventing blood loss) vs. potential harms (e.g. somewhat less good prediction).

The contribution of all of these baseline characteristics to the prediction of CCB were incorporated into a single score which was forced into models of laboratory predictors with a coefficient of 1.00 in order to enable comparisons between different models based on the various laboratory test platforms.

All laboratory measures from a platform were included for each model, with multivariable fractional polynomial techniques used to investigate the linearity of terms. All transformations and centering found to improve the fit of the models were implemented. Backward elimination was undertaken to select the final models with a threshold of inclusion of 0.05 and exclusion of 0.10. Initial models only considered the standard test results (see Table 2); subsequently the ‘early phase’ alternatives were considered for any terms that significantly contributed to the model.

The following models were constructed:

- **Model 2A:** pre-operative Multiplate in relation to **any CCB**
- **Model 2B:** pre-operative Multiplate in relation to **post-op CCB**
- **Model 2C:** post-operative Multiplate in relation to **post-op CCB**
- **Model 2D:** post-operative ROTEM in relation to **post-op CCB**
- **Model 2E:** post-operative TEG in relation to **post-op CCB**

Each model was then compared to a baseline model containing only the baseline characteristics in order to evaluate the contribution of the selected laboratory test results to the prediction of CCB. These are presented as receiver operating characteristic (ROC) curves.

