7.4.3 Analysis models

All outcomes listed in the study protocol will be presented as per the template tables [Table T7 to T8](#). General methods of presentation are outlined below.

⁷ i.e. factors associated with the both the laboratory test result(s) (exposure) and the outcome, unbalanced across the groups and not an intermediary step in the causal pathway from the exposure to outcome

The primary outcome (CCB) and secondary outcomes (any RBC transfusions > 4 units RBC transfusion, non-routine pro-haemostatic treatments, death, MI, any stroke, renal failure, AKI and infections during hospital admission) are all binary data.

These binary outcomes will be presented as numbers and percentages of patients. The association between laboratory test results and outcome will be quantified using logistic regression for binary data. Estimates will be presented as unadjusted and adjusted odds ratios (OR) and 95% confidence intervals (95% CI). For these binary outcomes analyses will only be performed if more than ten patients in total experience the outcome.

The sensitivity and specificity of laboratory test results to predict the outcome will be described for different thresholds and laboratory tests will be compared using the area under the receiver operating characteristic (ROC) curve.

The association between time of withdrawal of P2Y₁₂ blocker and laboratory test results will be described using linear regression.

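### The baseline score for the post-operative platform models contains no intra-operative duration, so the reported gain of the T3 tests may include information that bypass time already carries

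*SAP*

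**What the plan says.** Footnote 6 to section 7.2 lists the covariates of the Step 1 baseline model as a closed list. It opens with "age, sex, diabetic status (n/y), cardiac procedure (CABG only, CABG + valve, valve alone, other), operative priority (elective, urgent), eGFR, preoperative HCT" and closes with "treatment group, time since withdrawal (anti-platelet group), body mass index (BMI), preoperative platelet function and participation in another clinical study". The only surgical items are type of procedure and priority.

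Section 7.3 turns these characteristics into one score, enters it in each platform model with a coefficient of 1.00, and judges the platforms against it: "Each model was then compared to a baseline model containing only the baseline characteristics". The comparison is shown as ROC curves.

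Elsewhere the SAP looks wider. Section 2.3 states: "Other pre-operative, intra-operative and post-operative factors (up to T6) will be considered as potential confounders". Section 6.4 derives, under time in theatre, "Cumulative bypass time; cumulative cross-clamp time". The timeline in section 2.2 has "T1: cessation of CPB" and, two points later, "T3: time of post-op sample". Neither duration is named in section 2.7, in the expected relationships of section 7.1, or in any modelling step of sections 7.2 to 7.4.3.

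**The concern.** Section 2.1 attributes coagulation abnormality after cardiac surgery partly to what happens during the operation: dilution and inactivation of clotting factors and platelets, and increased clot breakdown. It links these abnormalities to bleeding. If a longer bypass run produces more of them, bypass duration is related both to the T3 test results and to CCB. It is also known, without any laboratory test, when the T3 sample is drawn.

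A score that leaves it out lets a T3 test stand in for it. Part of the AUC gain credited to ROTEM, TEG or post-operative Multiplate could then be the gain from knowing how long bypass lasted. At stake is what can be concluded about the value these tests add to information already in hand at T3.

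**Working it through.** **Reading the passages together**

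1. Is the list closed? Yes for the score: footnote 6 enumerates it, and sections 7.2 and 7.3 give no route for another item to enter.
2. Are the durations available in time? Yes. Bypass ends at T1 and the sample is taken at T3. Cross-clamping takes place within the bypass run.
3. Does the SAP's own definition of a confounder rule them out? No. Footnote 7 (section 7.4.2) requires a confounder to be "not an intermediary step in the causal pathway from the exposure to outcome". A duration that ends before the sample cannot lie between the test result and the outcome.
4. Are adjusters confined to pre-operative data by design? No. Section 2.7 puts the post-operative platelet count in all models.
5. Which models are affected? Models 2C to 2E, and Steps 3 and 4, which build on post-operative platforms. Models 2A and 2B use pre-operative Multiplate, when bypass time is not yet known, so a pre-operative score is right for them.

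**Illustration of direction**

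The SAP states no figure to reproduce. It gives no CCB rate and no association of bypass time with tests or outcome. All inputs here are assumptions: CCB 20% or 40%; odds ratio (OR) for CCB per SD of bypass time 1.0, 1.3 or 1.6; correlation of test with bypass time 0, 0.3 or 0.5; correlation of baseline score with bypass time 0.3 or 0.6 (0.6 at 20% CCB only), because procedure type is in the score; test OR per SD 1.0 or 1.3.

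With X the score, B bypass time and T the test (higher is worse), all standardised:

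- B = r_XB·X + √(1 − r_XB²)·e₁
- T = r_TB·B + √(1 − r_TB²)·e₂
- logit P(CCB) = a + 0.6·X + ln(OR_B)·B + ln(OR_T)·T, with a set to give the CCB rate

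Each scenario has 200,000 patients. The gain is AUC(X,T) − AUC(X) without bypass time and AUC(X,B,T) − AUC(X,B) with it. The simulation re-estimates the coefficient of X, whereas section 7.3 fixes the score's coefficient at 1.00, so this is a simplification.

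Results for a test with true OR 1.3:

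| CCB | OR_B | r_TB | r_XB | Gain without B | Gain with B | Test OR without B | Test OR with B |
|---|---|---|---|---|---|---|---|
| 20% | 1.3 | 0.3 | 0.3 | 0.019 | 0.010 | 1.396 | 1.306 |
| 20% | 1.3 | 0.3 | 0.6 | 0.015 | 0.009 | 1.372 | 1.308 |
| 20% | 1.6 | 0.5 | 0.3 | 0.033 | 0.007 | 1.600 | 1.306 |
| 20% | 1.6 | 0.5 | 0.6 | 0.020 | 0.006 | 1.523 | 1.305 |
| 40% | 1.6 | 0.5 | 0.3 | 0.034 | 0.007 | 1.597 | 1.305 |
| 20% | 1.6 | 0 | 0.3 | 0.012 | 0.010 | 1.300 | 1.309 |
| 20% | 1.0 | 0.5 | 0.3 | 0.013 | 0.010 | 1.302 | 1.306 |

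- Over all scenarios with OR_B 1.3 or 1.6 and r_TB 0.3 or 0.5, the gain is 0.015 to 0.034 without bypass time and 0.006 to 0.011 with it.
- In the same scenarios, a test with no effect of its own (true OR 1.0) shows an OR of 1.05 to 1.24 and an AUC gain of about 0.000 to 0.008. Both vanish once bypass time is in the baseline.
- The proxy matters. In rows 3 and 4, raising r_XB from 0.3 to 0.6 cuts the excess gain from 0.033 − 0.007 = 0.026 to 0.020 − 0.006 = 0.014.
- If bypass time is unrelated to the test or to CCB (the last two rows), the difference in gain is at most about 0.003. Even that is not confounding: a fuller baseline model leaves a little less to gain.

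**The case against.** The strongest reply is that this is a prediction study with an openly labelled comparator. Section 7.3 says that the contrast is with baseline characteristics only, and the gain over a pre-operative score is a legitimate quantity. Section 7.2 expects the post-operative platforms to win because they lie closer to the outcome, and carrying intra-operative information is part of what such a test does. All of that stands. It is why the pre-operative comparator should stay. It does not answer the question of value beyond what is known at T3, nor does it square with section 2.3.

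Four stronger readings are tempting and not supported:

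- *That the SAP shuts bypass time out of the adjusted odds ratios.* Section 2.7 is an open list, section 2.3 admits intra-operative factors, and section 7.4.2 retains a confounder on a likelihood ratio p-value below 0.05 or a change in the estimate above 10%. Bypass time could enter that way. The fair criticism is only that it is not named.
- *That the SAP defines the purpose of the platform analysis as deciding whether a test repays its cost.* The cost remark in section 7.2 explains only why variables are grouped by platform.
- *That Model 2B also needs bypass time.* It is a pre-operative test, and bypass time does not yet exist when it is run.
- *That the ranking among the post-operative platforms is wrong.* They share one score, and nothing here shows that their order would change.

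**Conclusion.** The gap is real and confined to the score of sections 7.2 and 7.3 as used for Models 2C to 2E and Steps 3 and 4. The SAP promises to consider intra-operative factors and derives two durations known before T3, but gives neither a place in the comparator. The gain of the post-operative tests over baseline may therefore be overstated as a measure of what they add at T3.

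A reader might infer from the simulation that the gains are overstated by a particular amount. The document does not support that. The direction rests on longer bypass worsening both test results and bleeding, which section 2.1 makes plausible but does not quantify. The size depends on associations that the SAP does not give and on how much of bypass duration the procedure type already captures. It could be close to nothing. This is an inexpensive improvement to what the analysis can show, and it does not invalidate the planned comparison.

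**What to change.** - Keep the pre-operative score for Models 2A and 2B, and as the existing common comparator.
- For Models 2C to 2E and Steps 3 and 4, define in footnote 6 and section 7.3 a second baseline score. It adds cumulative bypass time and cross-clamp time, with an indicator where bypass time is zero. Report the AUC change against both scores.
- In the Step 2 comparison with pre-operative Multiplate, also show the result with the extended score as a sensitivity analysis.
- Name the two durations in section 2.7 as candidate confounders for the adjusted odds ratios of T3 test results.

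Both variables are already derived, so the cost is an SAP amendment (logged as section 1.1 requires), one more score and a few more parameters. The price in results is probably a smaller reported gain for the post-operative tests. The gain over the pre-operative score is still shown beside it.
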